Power and Sample Size Considerations: The primary endpoint of this investigation is defined as the proportion of participants, in each intervention arm, who maintain the designated target weight loss of $\geq 5\%$ at 12 months from baseline. Additional power calculations were derived for the changes in absolute weight loss from 0-12 months and in fasting glucose levels from 0-12 months. For our primary endpoint of $\geq 5\%$ weight loss at 12 months, with $N = 160$ in each arm and assuming no more than 25% attrition, we have 80% power to detect differences of 19% between the two intervention conditions in the proportion of subjects achieving this weight loss target. There is 90% power to detect differences of 21% between the two groups. This translates to roughly half or more of the participants in the telephonic continued contact group maintaining $\geq 5\%$ weight loss compared to only about one-third of those in the newsletter control condition. These estimates are based on a Fisher's Exact test conducted at $\alpha = 0.05$ two sided with $N = 120$ in each arm. In addition, we also calculated power estimates for various differences in absolute weight loss (lbs) between GLB + 10TC and GLB + NC based on previous GLB outcomes presented in Table 2 (23). Assuming a two sample t-test conducted at $\alpha = 0.05$ two-sided with a standard deviation of 10.5 we find that there is 80% power to detect group differences of 3.8 lbs or 90% power to detect group differences of 4.4 lbs between the two arms at 12 months. Finally, for the secondary endpoint analysis of differences between GLB + 10TC and GLB + NC in fasting plasma glucose changes from 0-12 months and assuming a two sample t-test conducted at $\alpha = 0.05$ two-sided with a standard deviation of 11.9 based on data presented in Table 2 (23), we project that there will be 80% power to detect a difference of ≥ 4.3 mg/dl decrease or 90% power to detect a difference of ≥ 5.0 mg/dl decrease between the two intervention arms.

Hypothesis 3: GLB+10TC will be associated with more favorable weight, waist, glucose, lipid, blood pressure gait speed, grip strength, balance and HRQL (based on the physical component summary and the mental component summary scores from the SF-12v2®) compared to the GLB + NC group at 12- and 24-month follow up assessments.

Analysis Plan: We will compare GLB + 10TC and GLB + NC on changes in absolute and percent weight loss and each of the other outcome measures with a repeated measures mixed model. To test the treatment effect we will evaluate the coefficients associated with group and the group by time interaction. Planned contrasts will be constructed from the mixed model to evaluate differential changes in percent weight loss between the two conditions from baseline to post-treatment at 12 and 24 months. This procedure will be utilized for each of the other secondary measures.

An exploratory aim will be to evaluate direct program costs and self reported health care utilization.

Analysis Plan: The overall approach will be to report descriptive statistics, including the following: overall and component specific program costs, including allocation of time expenditures by screening staff and GLB interventionists, and the direct cost of all materials provided. For health care utilization we will summarize the self-reported number of times an individual has visited a physician/health care provider (outpatient), a hospital emergency room, the total number of separate hospital admissions, and the total number of nights spent in the hospital in the previous six months. Comparisons will be made between the two groups (GLB + 10TC and GLB + NC). Summary descriptive statistics will include mean, median, standard deviation and confidence intervals for continuous variables and proportions, ranges and percentiles for categorical variables.

[\[reviewer notes-\]](#)

2.19

Will this research be conducted in (a) a foreign country and/or (b) at a site (e.g., Navajo Nation) where the cultural background of the subject population differs substantially from that of Pittsburgh and its surrounding communities?

* No

Note that copies of training records, licenses, certificates should be maintained in the study regulatory binder and are subject to audit by the Research Conduct and Compliance Office (RCCO).

In addition, individuals planning to conduct human subject research outside the United States must complete an optional module on the CITI training website: International Studies. [Click here](#) to access the instruction sheet for accessing optional CITI modules.

[\[reviewer notes-\]](#)

2.21

Will this research study be conducted within a nursing home located in Pennsylvania?

* No

[\[reviewer notes-\]](#)

Section 3 - Human Subjects

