The current research can be classified as a feasibility/effectiveness design . First we will document the feasibility of community based implementation of an evidence-based 12-session Group Lifestyle Balance (GLB-12) intervention among retirees and/or their dependent spouses/partners who have enrolled or are about to enroll in Medicare benefits through the University of Pittsburgh. We will also recruit from other community locations. Following implementation of the non-randomized GLB-12, participants will be assigned by a stratified block randomization scheme to continued telephone contact (GLB + 8TC; N = 160) or to newsletter control (GLB + NC; N = 160) for the remainder of the one year intervention. Stratification will be based on the category of percent weight loss achieved during the first phase of intervention (<3.5 % and >3.5%). Major outcome assessments will be conducted at 0, 4, 12 and 24 months.

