- **duration of procedures**
- **timeline of study procedures**

Study Timeline

There will be at least three annual waves of recruitment. Baseline and annual assessments will be conducted in the period between January and March of each year; additional recruitment may occur between May and July of each year. Waves of intervention will commence within 8-12 weeks of screening and enrollment. Prior experience in our community based GLB projects indicates that these are optimal times to initiate programs. It will also allow for some groups to start in early Spring to accommodate older adults who travel during the winter months. If recruitment targets are lagging, there may be an additional wave of recruitment and intervention commencing in May/June annually---all procedures will be identical.

Training and Supervision.

The GLB-12 intervention will be administered in groups of approximately 15-20 participants

by three part-time lifestyle coaches, with Bachelor's degree training at minimum, and previous experience in health promotion, health education or lifestyle interventions. They will be trained by the Diabetes Prevention Support Center staff in a two-day workshop conducted by a nurse diabetes educator (CDE), registered dietitian, exercise specialist and a behavioral scientist. These individuals will be available for specialty consultation as needed. Each coach will conduct 3-10 groups (GLB-12) per year and be responsible for all associated follow up protocols. Drs. [name] and [name] will provide additional monitoring and supervision for the telephonic continued contact coaching protocol and each lifestyle coach will be required to audiotape 10% of their telephone contact sessions. Independent reviewers will complete a session content checklist of these recordings as an intervention fidelity check. If necessary, lifestyle coaches will be trained at remote campus locations to implement the GLB-12.

Description of GLB-12 session intervention.

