Following GLB-12, group telephone sessions will be the delivery format for the remaining one year of intervention. The content, structure and sequence of these sessions is similar to those conducted in person; however, a group phone coaching script and a participant handout will be developed that details norms and procedures for phone interactions. As with face-to-face intervention, the phone coaching sessions amplify core diabetes prevention and cardiovascular health messages and allow for continued weight, diet, and activity monitoring and accountability. Prior studies have shown that this method of coaching has been employed successfully both for initial standard (core) as well as maintenance interventions with older rural women (44, 45). All participants will be asked to call into a toll-free conference line, and to treat the weekly call time as a standing appointment for which they need to be in a private location free from distractions. Participants will be asked to dedicate a maximum of 45 minutes for actual phone call time, and to utilize 15 minutes post-call time to review home assignments on their own. In the GLB + 8TC condition, the first of the eight continued contact sessions be delivered face to face to orient those randomized to telephone continued care to the specific protocol and procedures, provide a new participant manual and other materials necessary to complete the remainder of the program. Because problem solving strategies will be a dominant focus of these continued contact sessions, we will limit participation on each group phone call to approximately 5-7 individuals. In addition, because of the critical importance of transitioning from face-to-face weekly sessions to home-based self-monitoring during the follow up phase, all GLB +8TC participants will be provided with a digital bathroom scale and a set of post-cards with instructions to mail in (or phone in) their weekly weights and physical activity minutes for the duration of the intervention.

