During these group phone consultations the participants will be encouraged to discuss their major barriers to achieving their dietary and physical activity goals and share the kinds of approaches/strategies that they have been attempting to use during the prior month, since the last contact. The specific information that is discussed/shared in these group interactions is at the discretion of each individual participant; the nature of these interactions is expected to be very similar to the types of discussions that occur in the live group interaction. Participants will not be asked to report their current weight or weekly physical activity minutes over the phone during the group interaction, although they will be asked to phone or mail this specific information in to their lifestyle coach monthly .

GLB followed by Newsletter only (GLB+ NC). Following GLB-12, four newsletter packets containing information related to general health and well being (as opposed to specific behavioral diet, weight loss and activity messages) will be mailed to participants at month 6

and month 11 from baseline. The packets will also include reminders about pending assessments, and colorful, professional quality pamphlets and brochures from the National Institute on Aging (NIA) that pertain to the self-management of sleep, stress, arthritis and osteoporosis.

2.6.1

Will blood samples be obtained as part of this research study?

* Yes

*If submitting a protocol for expedited review, it should be clear that the planned blood draws are within the parameters described here:
<http://www.hhs.gov/ohrp/policy/expedited98.html> (see Expedited Research Category #2)

If **Yes**, address the frequency, volume per withdrawal, the total volume per visit, and the qualifications of the individual performing the procedure:

Fasting Glucose and Lipids (total, HDL and LDL cholesterol, and triglycerides): will be collected via finger stick sampling after at least an 8 hour fast (last food/drink consumption will be documented prior to collection of sample). We will use the Cholestech LDX® System, with results available immediately, and adhere to all quality control measures published by the Cholestech Company. Each procedure requires no more than one or two drops of blood or 40 ul (microliters) or less than one teaspoon maximum. The person completing the procedure will be either a trained phlebotomist or other medical technician.

Study Flow Chart:

Name

Modified Date

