All analyses will be conducted in consultation with [name], the study biostatistician. Descriptive analyses and graphic displays will be used to identify outliers, missing data and patterns of attrition that will guide decisions about the use of transformations and appropriate tests. Demographic variables and baseline measures will be compared between the GLB+10TC and GLB+NC conditions. In all outcome analyses we will use an intent-to-treat (ITT) approach in which participants remain in the study arm to which they are randomized regardless of attrition. The primary analytic strategy will be a mixed models approach in which treatment group, time, and time by group interaction are treated as fixed effects, and subject and percent weight loss during the first phase of intervention (<3.5% and >3.5%) are treated as a random effects to account for individual subject variability. Hypothesis tests will be two-sided and significance will be set at the 0.05 level. Analytical tools will include SAS (SAS Institute, Inc., Cary NC), Stata (StatCorp LP, College Station, TX) and StatXact (Cytel, Inc. Cambridge, MA). Mixed models are applicable to longitudinal datasets that contain missing observations, with

the assumption that the data are considered to be missing at random (MAR) or ignorable missing. Although we will be proactive in maximizing subject retention, we anticipate 75% adherence over the 12-month intervention period. Those who drop out or are lost to follow-up will be compared to those who have completed intervention sessions and research assessments using standard parametric and non-parametric methods, as appropriate. We will examine the patterns of missingness and, if necessary, account for missingness in outcome analysis (e.g., the covariate approach). Finally, regression modeling will be conducted to adjust for covariates, including demographic variables such as age, race, sex, number of sessions completed, as well as any other variables that have been found to differ across treatment conditions at baseline.

Research Questions

Hypothesis 1 (feasibility): On average, we will enroll ≥ 107 participants per year for each of three years to GLB-12; they will complete $> 65\%$ of sessions, return $\geq 50\%$ of self-monitoring records and report above average program satisfaction at the 4-month assessment.

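### Only the telephone arm is treated in small groups, and neither the Hypothesis 3 model nor the power calculation allows for phone-group correlation; the effect is negligible to modest

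*Combined protocol and SAP*

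**What the plan says.** Section 2.6 has two layers of grouping. Before randomization, everyone attends in-person groups: "The GLB-12 intervention will be administered in groups of approximately 15-20 participants". On staffing it says: "Each coach will conduct 3-10 groups (GLB-12) per year and be responsible for all associated follow up protocols". After randomization only the telephone arm is grouped: "we will limit participation on each group phone call to approximately 5-7 individuals" (repeated in 2.7). These calls are interactive; section 2.6 says that "participants will be encouraged to discuss their major barriers to achieving their dietary and physical activity goals and share the kinds of approaches/strategies". The comparator receives mailed newsletters.

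Allocation is by individual. Section 2.3 says "participants will be assigned by a stratified block randomization scheme to continued telephone contact", and "Stratification will be based on the category of percent weight loss achieved during the first phase of intervention". GLB-12 group is not named as a stratification factor.

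In 2.18 the mixed model has arm, time and their interaction as fixed effects. Subject and first-phase weight-loss category "are treated as a random effects to account for individual subject variability". Hypothesis 3 compares the arms on weight change and "each of the other outcome measures with a repeated measures mixed model". The power text in 2.18 uses Fisher's exact test and two-sample t-tests with 120 analysed per arm; 3.12 repeats the Fisher part. Neither section mentions an ICC, a design effect, or a term for phone group or GLB-12 group.

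**The concern.** People who share a call discuss the same problems with the same coach and peers, so their outcomes may become alike. That can happen in one arm only, which makes this a partially nested design. A subject random effect handles repeated measures on one person, not likeness between members of the same call. If such correlation exists, the telephone-arm mean is less precise than the model assumes. Confidence intervals for the arm difference are then too narrow, and stated power is somewhat high. Hypothesis 3 covers many continuous outcomes at months 12 and 24, and each carries the same omission. If group identifiers are not kept, the correlation can be neither estimated nor adjusted for later.

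**Working it through.** **Inputs from the documents.** 160 randomized per arm, 25% attrition, 120 analysed; two-sided alpha 0.05; SD 10.5 lb and 11.9 mg/dl; 80% power stated for 3.8 lb, 4.3 mg/dl and 19 percentage points; control rate about one-third; 5-7 per call.

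**Assumed.** The phone-specific ICC *r*, taken as 0.02, 0.05 and 0.10, and equal total variance in the two arms.

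**Group size.** 160/7 to 160/5 gives about 23 to 32 phone groups. After attrition, 5 × 0.75 = 3.75 to 7 × 0.75 = 5.25 are analysed per group. The midpoint is *m* = 4.5.

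**Stated power under independence.** Power = Φ(d / (SD·√(2/120)) − 1.96).
- Weight: 3.8/(10.5 × 0.1291) = 2.803, so power is 80.0%.
- Glucose: 4.3/(11.9 × 0.1291) = 2.799, so power is 79.9%.
- Exact Fisher power from 1/3 for 19 points: 81.8%.

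The stated 80% figures reproduce. Those for weight and glucose leave no slack.

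**Phone-specific correlation, none inherited from GLB-12.** The telephone-arm variance is multiplied by DE = 1 + (m−1)r. The variance of the difference is multiplied by f = (1 + DE)/2. Type I error of the unadjusted test is 2[1 − Φ(1.96/√f)]. Adjusted power is Φ(d/(SD·√(2f/120)) − 1.96).

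| m | r | f | Type I error | Power, 3.8 lb | Power, 4.3 mg/dl |
|---|---|---|---|---|---|
| 4.5 | 0.02 | 1.035 | 5.4% | 78.7% | 78.6% |
| 4.5 | 0.05 | 1.0875 | 6.0% | 76.7% | 76.5% |
| 4.5 | 0.10 | 1.175 | 7.1% | 73.4% | 73.3% |
| 5.25 | 0.10 | 1.2125 | 7.5% | 72.1% | 72.0% |

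**Adding correlation inherited from GLB-12 groups (ICC *g*).** This correlation reaches both arms.
- If the arms are evenly split within GLB-12 groups, the shared effect cancels from the difference, but the unadjusted test still counts it as noise. Then f = 1 − g + (m−1)r/2, which exceeds 1 only when (m−1)r > 2g. At m = 4.5 that means r > 2g/3.5 = 0.57g. Below that point the unadjusted test is slightly conservative.
- If allocation ignores GLB-12 group, as in simple randomization, f stays at about 1 + (m−1)r/2, so any positive r is enough.

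Illustration with an assumed g = 0.05 and m = 4.5:

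| r | f, even split | Type I error, even split | Type I error, no balance |
|---|---|---|---|
| 0.02 | 0.985 | 4.8% | 5.4% |
| 0.05 | 1.0375 | 5.4% | 6.0% |
| 0.10 | 1.125 | 6.5% | 7.1% |

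**Primary endpoint.** Exact enumeration, control rate 1/3, telephone arm as beta-binomial groups (12 of 5 and 15 of 4, total 120), r = 0, 0.02, 0.05, 0.10.
- Size of Fisher's test: 3.6%, 3.9%, 4.5%, 5.4%.
- Power for 19 points: 81.8%, 81.4%, 80.8%, 79.9%.

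For a cluster-adjusted binary test, take the deviate that matches 81.8% power, 0.907 + 1.96 = 2.867. Divide it by the square root of [p₁(1−p₁)DE + p₀(1−p₀)] / [p₁(1−p₁) + p₀(1−p₀)], with p₁ = 0.523 and p₀ = 0.333. At r = 0.02, 0.05 and 0.10 power is about 80.4%, 78.3% and 75.0%.

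**The case against.** The strongest reply is that the effect may be very small. The documents give no ICC, and exposure to the phone group is limited. Of the eight sessions the first is face to face, which leaves seven scripted calls of at most 45 minutes. Weights and activity minutes are not reported during the call. Fixed membership of phone groups is not stated; the standing-appointment wording only suggests it. Month 24 falls about a year after intervention ends. All this stands, and it is why an ICC near 0.02 or below, where the effect is negligible, is quite possible.

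Four stronger readings are tempting, and the documents do not support them.
- A reader might infer that any phone-group correlation inflates false positives. With arms evenly split within GLB-12 groups it need not. The documents do not say whether the split is even, or whether phone groups are formed within GLB-12 groups.
- A reader might infer the reverse: that phone-specific correlation must exceed the inherited correlation before it matters. Even with an even split, 0.57 of the GLB-12 ICC is enough at 4.5 per call.
- A reader might take six analysed per call and obtain larger effects. But 120/6 = 20 groups implies 160/20 = 8 randomized per call, above the stated 5-7.
- A reader might infer that the primary comparison is unsound. Fisher's test is conservative enough to absorb most of the correlation. Its size reaches only 5.4% at ICC 0.10.

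Finally, the figures are for single-visit tests on 120 per arm. The power of the repeated-measures model, which keeps participants with missing visits, was not computed.

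**Conclusion.** The omission is real, and nothing elsewhere in the documents closes it. Its size is conditional: negligible up to a phone-specific ICC of about 0.02 and modest beyond. At 0.05-0.10 with 4.5 analysed per call and no inherited correlation, power for 3.8 lb falls about 3 to 7 points below the stated 80%; at the upper limit of 5.25 per call and ICC 0.10 it falls about 8 points. Inherited GLB-12 correlation combined with even splitting reduces the false-positive excess and can reverse it. For the primary endpoint the cost lies mainly in the power of a cluster-adjusted analysis, not in the validity of Fisher's test. The conclusion rests on assumed ICCs, equal variance in the two arms, and phone groups stable enough to induce correlation. This is a cheap improvement worth making, not a threat to the trial's main comparison.

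**What to change.** 1. State how phone groups are formed and whether membership is fixed. Record each participant's assigned GLB-12 group and assigned phone group.
2. In the Hypothesis 3 models (2.18), add a random phone-group effect in the telephone arm only, with newsletter participants as singletons, and a random GLB-12 group effect in both arms. Use a small-sample degrees-of-freedom correction. Keep the GLB-12 term whether or not phone groups cut across GLB-12 groups, because both arms share that correlation either way.
3. Report a cluster-adjusted analysis of the binary 5% weight-loss endpoint alongside the planned one.
4. In 2.18 and 3.12, say that the power figures assume no phone-group correlation. Give them, for the measures each section covers, over a phone-specific ICC range labelled as an assumption (for example 0.01-0.10) at the post-attrition group size.

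**Cost.** Analysis-plan wording, two identifier variables, and slightly lower stated power. If there is no clustering, the extra terms cost about 1.4 points: in a simulation with 16 GLB-12 groups of 15 analysed, power for 3.8 lb was 79.0% with both terms and 80.4% for the t-test. No extra participants are needed.

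### The Hypothesis 3 contrasts at 12 and 24 months adjust no outcome for its own continuous month-4 value, which very probably precedes randomization, so some precision is given up

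*Combined protocol and SAP*

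**What the plan says.** Section 2.3 gives the order of events: "Following implementation of the non-randomized GLB-12, participants will be assigned by a stratified block randomization scheme". The strata are two categories of first-phase percent weight loss, split at 3.5%. Major assessments are at months 0, 4, 12 and 24.

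Section 2.18 describes the main model as a "mixed models approach in which treatment group, time, and time by group interaction are treated as fixed effects". Of the random effects it says that subject and "percent weight loss during the first phase of intervention (<3.5% and >3.5%) are treated as a random effects". A later regression step adjusts for demographics, number of sessions completed and "any other variables that have been found to differ across treatment conditions at baseline".

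The Hypothesis 3 analysis plan compares the arms "on changes in absolute and percent weight loss and each of the other outcome measures with a repeated measures mixed model". On the test itself it says: "To test the treatment effect we will evaluate the coefficients associated with group and the group by time interaction". Planned contrasts then evaluate "differential changes in percent weight loss between the two conditions from baseline to post-treatment at 12 and 24 months", and the plan adds: "This procedure will be utilized for each of the other secondary measures".

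No section adjusts an outcome for its own continuous month-4 value or holds the arms equal before randomization. The plan does not say which visits enter the model as responses.

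**The concern.** Both arms receive the same programme up to month 4, so a month-4 measurement taken before allocation is a baseline for the randomized comparison. It is also the baseline closest in time to the 12- and 24-month outcomes. Adjusting for it removes variation that has nothing to do with the randomized treatment.

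The planned model uses little of this information:

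- **The stratum.** It is a two-level cut of weight loss and does not carry month-4 glucose. Entered as an additive effect common to all visits, it cancels from a change-from-baseline contrast.
- **Month 4 as a response.** If the group-by-time means are free, month 4 contributes nothing to the 0-12 contrast with complete data, and only part of the possible gain with missing data.
- **The covariate regression.** It does not name month-4 values, and selecting variables because they differ at baseline does not guarantee that they enter.

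The stake is wider confidence intervals than necessary for Hypothesis 3.

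A secondary point concerns the separate test of the group coefficient. If pre-randomization visits are modelled as responses, that coefficient can reflect a chance baseline difference (month 0 as the reference) or a diluted effect.

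**Working it through.** **Inputs from section 2.18.** Two-sided alpha 0.05; 160 per arm with 25% attrition, so 160 × 0.75 = 120 per arm; SD 10.5 lb for weight change and 11.9 mg/dl for glucose change over 0-12 months.

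**Assumed.** r, the correlation between the 0-4 and 0-12 month changes, at 0.3, 0.5 and 0.7.

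**Step 1: reproduce the plan.** Detectable difference = SD × √f × (1.960 + 0.842) × √(2/120), where f is the variance relative to the unadjusted change score. With f = 1:

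- Weight: 10.5 × 2.8016 × 0.1291 = 3.80 lb (plan: 3.8).
- Glucose: 11.9 × 2.8016 × 0.1291 = 4.30 mg/dl (plan: 4.3).

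**Step 2: f for each model.**

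- Four visits as responses, arms unconstrained, complete data: f = 1. Month 4 adds nothing, whatever r is.
- The same with 160 per arm and 120 seen at month 12: per-arm variance is SD² × [(1 − r²)/120 + r²/160], so f = 1 − 0.25r².
- Change score with the stratum fully used, cut assumed at the median: f = 1 − (2/π)r².
- Continuous month-4 value as a covariate: f = 1 − r².

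**Step 3: detectable 12-month weight difference (lb), 80% power.**

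| Model | r = 0.3 | r = 0.5 | r = 0.7 |
|---|---|---|---|
| Unadjusted, or four visits unconstrained with complete data | 3.80 | 3.80 | 3.80 |
| Four visits unconstrained, 25% missing | 3.75 | 3.68 | 3.56 |
| Change score with stratum | 3.69 | 3.48 | 3.15 |
| Continuous month-4 value | 3.62 | 3.29 | 2.71 |

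The equivalent saving in patients is 1 − (1 − r²)/f. Against the stratum model it is 3.5%, 11% and 26%. Against the unconstrained four-visit model with 25% missing it is 7%, 20% and 42%.

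For glucose, adjustment for its own month-4 value gives 4.11 mg/dl at r = 0.3 and 3.73 at r = 0.5, against 4.30 unadjusted.

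**Step 4: does a constrained four-visit model do as well?** This check uses generalized least squares with complete data and 120 per arm. Assumed SDs are 35 lb at baseline, 8 lb for the 0-4 change and 10.5 lb for the 0-12 and 0-24 changes. Changes are taken as unrelated to baseline, with a 12-24 month correlation of 0.7.

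- Arms held equal at months 0 and 4, correct covariance: 3.62, 3.29 and 2.71 lb, the same as the covariate model.
- The same constraint with a random subject intercept only (compound symmetry): 3.64, 3.33 and 2.99 lb.
- Arms held equal at month 0 only: 3.80 lb at every r.

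**Step 5: bias.** A simulation of 4000 trials per r had a true effect of 3.8 lb and 25% missing at random depending on the 0-4 change. Mean estimates lay between 3.78 and 3.83 lb for every model, so the difference between models is precision only.

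**The case against.** **No error is shown.** The planned contrasts are valid, and the primary endpoint (the proportion keeping at least 5% weight loss at 12 months) is untouched. A reader might infer that the planned comparison is biased or the trial underpowered. The documents support neither: the stated power figures come from unadjusted tests and reproduce. This objection stands, and it sets the priority.

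**The size is assumed.** No r is given. At r = 0.3 the step from the stratum model is 3.69 to 3.62 lb, and the larger savings need a high r. A reader might carry the figures over to month 24 or to waist, lipids, function and quality of life. The documents give no SD for those outcomes, and no SD, attrition or correlation for month 24, so no figure is offered. This stands.

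**The timing is inferred.** A reader might take it as stated that month 4 precedes allocation. Section 2.18 treats 0-4 months as before-to-after the non-randomized phase, and the stratum needs an end-of-phase weight. But section 2.6 separates session weights from research weights, and the stratum could come from the former. The study flow chart that might show the order is not reproduced in the public file. If month 4 follows allocation, adjusting for it could remove part of the treatment effect. The order must be confirmed first.

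**The plan partly covers it.** For weight, full use of the stratum recovers 2/π, or 64%, of the available variance reduction. The covariate list is also open-ended. Neither secures adjustment for each outcome's own month-4 value.

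**The group-coefficient point depends on coding that the plan does not state.** That is so, and contrasts at 12 and 24 months are already planned. A reader might infer that the plan certainly tests a baseline difference; it is only a possibility left open.

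**Conclusion.** The point holds as a missed gain in precision. On the reading that month 4 precedes allocation, the Hypothesis 3 model uses month-4 information only through a two-level weight-loss category, although each outcome's continuous value at that visit would serve better.

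For 12-month weight change the detectable difference at 80% power would move from 3.80 lb to 3.62, 3.29 or 2.71 lb at r = 0.3, 0.5 or 0.7. Measured from a model that fully uses the stratum, the gain is smaller, and slight at r = 0.3. It vanishes at r = 0. These figures rest on the plan's SD and attrition, an assumed r and, for the stratum comparison, an assumed median split. Low priority.

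**What to change.** 1. Confirm and state that the month-4 assessment is completed before allocation.
2. If so, model months 12 and 24 as responses with group, visit, group-by-visit, the stratum, and that outcome's month-0 and continuous month-4 values.
3. For percent weight loss, use baseline weight and continuous month-4 percent loss as covariates, because the month-0 value is zero for everyone.
4. If a four-visit model with the arms held equal at months 0 and 4 is preferred, use it for absolute measures only and specify an unstructured covariance. A random subject intercept alone gives only part of the gain.
5. If month 4 proves to follow allocation, adjust for month 0 only and expect little or no gain for weight.
6. Name the between-arm contrasts at months 12 and 24 as the test of treatment effect, in place of the separate group coefficient.

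The cost is model wording, code and one sentence on visit order; no new data are needed. Missing month-4 covariates need simple handling under step 2. How many there will be cannot be judged from the documents.
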